- Support and follow-up measures such as protocolized telephone follow-up and telemonitoring improve adherence. (Ruiz-López, 2009; Rotenberg, Murariu, Pang, 2016)
- The Adhesion Improvement Plan based on a cost-effectiveness balance achieves better adherence results. (Ibarra, Morillo, Rudi, Ventura, Navarro, 2013).

METHODOLOGICAL SECTION

1. Design. Experimental, prospective and controlled study. All participants will sign informed consent after knowing in depth the objectives, methods and risks of the study. The CONSORT Criteria for non-pharmacological trials will be followed (Boutron, Moher, Altman, Schulz & Ravaud, 2008).

2. Sample size: The sample size is defined by the research design, in which the subjects are randomly distributed to the two experimental conditions, that is, the Control Group and the PIMA Group. It is thus necessary to determine at the beginning the minimum size of the groups based on the following factors. Taking into account that the intervention process is based on the motivational interview, in the first place, we establish a type I error of 0.05, and a type II error of 0.20 (power = .8), as is usually assumed in research in the framework of the study of the therapeutic efficacy of motivational / psychological interventions (Hair, Anderson, Tathan & Black, 1999). On the other hand, reviews of previous research on the efficacy of motivational / psychological interventions on the outcome variables to be considered (behavioral change / adherence, quality of life), revealed that there are hardly any studies of this nature, without detail data on standardized effect size that serve as a starting point in defining, among other aspects, the ideal sample size for our research. Due to the characteristics of the existing studies (Edelman, Bell and Kidman, 1999; Edelman, Lemon, Bell and Kidman, 1999; Goodwin et al. 2001), we observed effect size values around 0.50. In addition, for a study such as the one proposed in this study, a sufficient number of subjects is required to allow observing and assuming the normality of the scores in the variables considered, as well as performing multivariate analyzes, with a sufficient number of observations to carry them out.

[figure not shown]

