finished. For all the above considerations, we conclude that around 33 subjects per group would be the size of the sample necessary to assess the therapeutic efficacy of the interventions developed. On the other hand, we take into account the type of patient we are dealing with, who may be abandoned, for which a number of 35 subjects per group is established (anticipating a certain experimental mortality). The design effect size as defined is $d = 0.60$, which is a moderate effect size.

3. Stages of the study:

3.1. Referral / recruitment phase and randomization. In patients diagnosed with OSA, 2 groups of at least 35 patients will be constituted. Following the CONSORT Criteria (Boutron, Moher, Altman, Schulz & Ravaud, 2008) for non-pharmacological trials, the randomization method has been selected through a simple method: each time the prescribers evaluate the sleep test, they include in one of the two groups according to the following randomization algorithm: each patient is assigned to a group alternatively, that is, one patient is assigned to the Control group and the next to the PIMA group; This sequence is followed in 6 pairs, being that the following 6 pairs were assigned starting with one patient to the PIMA group and another to the Control group later. This allocation mechanism is also the one used to compensate for experimental mortality in both groups. In this way 2 groups will be configured:

- 1) Control Group or PIMA 0, which will start treatment with regular CPAP WITHOUT stratification;
- 2) PIMA 1 Group, which will start treatment according to stratification; This will be the result of a comprehensive initial evaluation and the result of stratification.

3.2. **Stratification process:** To achieve stratification, two types of variables are taken into account that the bibliography indicates influence the treatment of CPAP: personal variables and modulating variables. Personal variables are those that refer to patient characteristics. These are grouped into 4 categories: protective factors, risk factors, clinical factors and motivation (in the case of OSA). The following figure shows the set of variables used for patient stratification, and their relationship with individualized protocols.

Regarding the modulating variables, these refer to the characteristics of both the patient's environment (distance between the patient's home and the hospital) or relative to options and

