The monitoring and visualization of the alerts will be carried out with a determined periodicity: Day 10, Day 20, Day 30 of the period after low adherence detection. The alerts (situations that imply poor evolution and need to notify the prescriber) are the following:

- - Hours <4
- AHI> X + Hours <4
- IAH> X + Hours> 4
- Leaks> Y

Prescribing physician information report: a report is extracted in PDF format that is reported to the prescribing physician.

3.1. Monitoring and control of adherence. All measurements will be performed in 4 times: Day 1 - Day 30 - Day 60 - Day 90 – Day 180. In the Control Group, the usual methodology of treatment with CPAP will be used. In PIMA 1 Group, the methodology will be used according to the Individualized Adherence Improvement Plan arising from stratification.

3.2. Analysis of results.

Descriptive variables (characterize the sample used and make the study replicable and transparent, thus contributing to generalization). Study of initial homogeneity: categorical variables (χ^2) + associated effect size. Quantitative variables: Student's t test for independent samples, correction (Levene's test).

- Hypothesis:
 - T-tests of means of related samples (to know if through the different interventions there are improvements in adherence and quality of life, they report the effects on the outcome variables)
 - Model of structural equations (to know the relationships between protection and risk factors and educational, training and technological actions)

- Independent samples t-test (know the significance associated with the differences between the two interventions)
- Analysis of variance (ANOVA) (differences were due to the type of intervention in combination with some other categorical variable)
- Linear correlations (know the interrelation between the so-called gains or aspects of change of the 2 interventions)
- Effect size:
 - or (Cohen's $d = t / rN$) (value exceeds 0.30, which is equivalent to a moderate-high effect size, greater in any case than 0.60)

3.1. Subjects of study.

Inclusion criteria: Being over 18 years of age, OSA diagnosis for whom CPAP treatment has been prescribed)

Exclusion criteria:

- Hypoventilation obesity
 - severe COPD
 - (FEV1 (%) = <50%)
 - mMRC > 2
 - Cognitive disorders
 - ICC (NYHA: Grade III and IV)
 - or reject

4. Variables

- **Sociodemographic variables:** age, gender, marital status, educational level, ...

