The principal investigators of this Study guarantee that all the participants have assumed generic confidentiality obligations regarding the information they access in the performance of their duties.

SCHEDULE

Activity / Task

Recruitment, constitution of study subgroups, obtaining clinical and functional information, clinical review of participants.

J	F	M	A	M	J	J	A	S	O	N	D
				X	X	X	X				

Activity / Task

Comprehensive evaluation of patients. Educational process. PIMA identification.

J	F	M	A	M	J	J	A	S	O	N	D
				X	X	X	X	X			

Activity / Task

Cross-sectional analysis of results

J	F	M	A	M	J	J	A	S	O	N	D
								X	X		

Activity / Task

Longitudinal analysis of results

J	F	M	A	M	J	J	A	S	O	N	D
									X	X	X

EXPERIENCE OF THE RESEARCH TEAM ON THE TOPIC

The clinical team of Hospital Universitario La Princesa maintains a specific and continuous care activity, being a reference in the area for the treatment of sleep.

VitalAire, Air Liquide Healthcare's therapy activity, has been in home respiratory therapy treatments for more than 30 years.

DIFFUSION PLAN

1) Clinical impact, assistance and / or technological development. This project has a great impact and clinical and technological significance. From a clinical point of view, the aim is to identify the patient in order to better serve him and ensure adherence to one of the treatments where it is more complex to achieve patient compliance.

2) Bibliometric impact. This project is expected to lead to world-class, high-impact publications.

3) Technological development. This project includes the development of computer applications that allow optimization of resources and better assistance.

RESOURCES AVAILABLE TO CARRY OUT THE PROJECT

Consult "Punto Inspira" located in the Hermanos García Noblejas Specialty Center, belonging to the La Princesa University Hospital area.

Resources of VitalAire, concessionary company of home respiratory therapies of the Hospital Universitario de La Princesa: healthcare personnel, computer, telephone, data line, specific applications, transport vehicles, educational material ...

ANEX

Informed consent sheet for the patient complying with the regulations in this regard.

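### Adherence is measured at four follow-up days, but no listed between-arm method combines them or names the visit or summary to be tested

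*Combined protocol and SAP*

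**What the plan says.** **Measurement times.** Section 3.1, Monitoring and control of adherence: "All measurements will be performed in 4 times: Day 1 - Day 30 - Day 60 - Day 90", with Day 180 following in the same list. The count is four and the list has five entries. If Day 1 is the start of treatment, four entries are follow-up, but the text does not say so.

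**Between-arm methods.** Section 3.2, Analysis of results, gives "Independent samples t-test (know the significance associated with the differences between the two interventions" and an ANOVA of intervention with a further categorical variable that is not identified. No visit, summary over visits or time factor is named. The other methods are paired t-tests of change, correlations between gains, and a structural equation model of factors and actions. None is described as comparing the arms over all visits.

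**Longitudinal work.** The Schedule reserves October to December for "Longitudinal analysis of results". No method is attached to it.

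**Design figures.** Under Sample size: "we establish a type I error of 0.05, and a type II error of 0.20 (power = .8", "around 33 subjects per group would be the size of the sample necessary" and "The design effect size as defined is $d = 0.60$, which is a moderate effect size". The number is then raised to 35 per group for dropout. Sidedness is not stated.

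**Outcome.** Use is read from the CPAP hour meter (Summary), with no averaging window. The main goal takes 3.5 hours per night as the criterion for adherence, without saying whether mean hours or a yes/no result is analysed.

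**The concern.** A t-test takes one value per patient. With several follow-up readings and no rule for choosing or combining them, the plan leaves the main comparison open. One route is a single visit, chosen at some unstated moment. The other is a test at every visit with no adjustment, which raises the chance of a false positive and leaves open which result counts.

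Precision is also at stake. With 70 patients, a contrast averaged over visits can be more precise than a comparison at one visit. A repeated-measures model also keeps patients who have early readings but no last one, under a missing-at-random assumption. The Sample size section itself expects some loss.

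**Working it through.** **1. The plan's own figure.** Inputs: type I error 0.05, power 0.80, d = 0.60, and d about 0.50 from earlier studies ("we observed effect size values around 0.50"). Required n per group from the t distribution:

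- two groups, d = 0.60, two-sided: 44.6, so 45
- two groups, d = 0.60, one-sided: 35.0
- two groups, d = 0.50, two-sided: 63.8, so 64
- paired test, d = 0.50, two-sided: 33.4

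The stated 33 is approached by a one-sided two-group test at 0.60 or a paired formula at 0.50. A two-sided two-group test does not give it. What follows takes d = 0.60, 35 per arm and a two-sided test.

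**2. One visit.** Noncentrality = d × √(n/2) = 0.60 × √17.5 = 2.51 on 68 degrees of freedom. Power is 69.7%, or 80.0% if the test is one-sided.

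**3. Average of four visits.** For k equally correlated visits, the variance of a patient's mean relative to one visit is f = (1 + (k − 1)ρ)/k. The effective d is 0.60/√f and the equivalent n per arm is 35/f. The documents give no ρ, so the values below are assumptions.

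| ρ | f (k = 4) | effective d | power | equivalent n | gain per arm |
|---|---|---|---|---|---|
| 0.5 | 0.625 | 0.759 | 87.9% | 56.0 | 21.0 |
| 0.7 | 0.775 | 0.682 | 80.3% | 45.2 | 10.2 |
| 0.9 | 0.925 | 0.624 | 73.0% | 37.8 | 2.8 |

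With three visits and ρ = 0.7, f = 0.80 and power is 79.0%. With d = 0.50 at every visit, one visit gives 54% and four visits give 65% at ρ = 0.7.

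**4. When the effect is not constant.** The averaged contrast beats a test at a visit with d = 0.60 only if the mean d over visits exceeds 0.60 × √f. That is 0.474, 0.528 or 0.577 at ρ = 0.5, 0.7 or 0.9. Two illustrations at ρ = 0.7:

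- d = 0.30, 0.40, 0.50, 0.60: mean 0.45, effective 0.45/√0.775 = 0.511, power 56%, against 70% at the last visit
- d = 0.45, 0.50, 0.55, 0.60: mean 0.525, effective 0.596, power 69%, so no gain

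**5. Unadjusted tests at four visits.** I simulated 35 per arm, normal data, equal correlation and no true effect, with 200,000 runs for each ρ. The chance of at least one two-sided p below 0.05 was 15.5%, 13.1% and 9.3% at ρ = 0.5, 0.7 and 0.9. Four independent tests would give 1 − 0.95⁴ = 18.5%.

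**The case against.** The strongest reply is that the gain comes from changing the question. Averaging over follow-up is a different target from the effect at Day 180. With complete data, a model with arm-by-visit terms and unstructured covariance adds essentially nothing at Day 180 alone. A constant effect cannot be presumed either: telemonitoring starts only after a low-adherence label, with alerts viewed at Days 10, 20 and 30 from then. This stands, and step 4 shows that the gain can disappear or reverse.

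Second, a t-test on each patient's mean over follow-up is not excluded. Step 3 is in effect that test, so with complete data it does not show that a mixed model is needed. This also stands. What the plan lacks is the statement of which value is tested.

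Third, the outcome may not fit the calculation. If the meter reading accumulates from the start, one late reading already averages all nights and the gain shrinks. If adherence is analysed as yes/no at 3.5 hours, the figures for means do not apply directly. The documents settle neither point.

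A reader might infer that the repeated readings go unused. The documents do not support that: paired t-tests and correlations of gains use them, a longitudinal analysis is scheduled, and the unnamed ANOVA factor could be visit. The gap is that no between-arm method combining visits is specified.

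**Conclusion.** The point holds as a gap in specification. No listed between-arm method combines the follow-up values or says which visit or summary is tested, and the scheduled longitudinal analysis has no method.

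Two firmer conclusions are tempting and should not be drawn. One is that the readings are worth about 10 patients per arm. That needs a between-visit correlation near 0.7, equal correlations, and d = 0.60 at every visit; over correlations of 0.5 to 0.9 the figure runs from about 21 down to about 3. The other is that the trial's false-positive rate is 9% to 15%. That applies only if four unadjusted tests are run and any one is taken as success, which the plan permits by silence but does not state.

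The case for change does not depend on the power gain. One pre-stated contrast removes the choice of visit. The change should be made.

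**What to change.** - Reconcile the count of measurement times with the list, and state which are follow-up.
- State that hours per night are computed for each interval between visits, and whether the main adherence analysis uses hours or the yes/no criterion.
- For hours per night, replace the separate t-tests by one linear mixed model on Days 30, 60, 90 and 180, with arm, visit, arm-by-visit and unstructured within-patient covariance.
- Pre-state one main contrast: the arm difference averaged over the follow-up visits. State the weights, since the last interval covers 90 days and the others about 30.
- Report the Day 90 and Day 180 differences with confidence intervals from the same model.
- Use the same model for quality of life, with the Day 1 score as covariate.
- Name this model as the method for the longitudinal analysis in the Schedule.

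The cost is analysis text only, with no added patients, visits or procedures. The downside is that the averaged effect is not the Day 180 effect, and it loses power if the benefit is concentrated at one visit. The visit-specific differences show whether the effect fades or grows.

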
HYPOTHESIS

The stratification / segmentation of the patient allows the elaboration of an individualized plan to improve adherence to treatment with CPAP, using telemonitoring for a specific profile; this stratification improves adherence to CPAP treatment of sleep apnea.

OBJECTIVES

Main goal:

- Improve adherence to CPAP treatment. To measure this variable, the definition of adherence / compliance with SEPAR is taken as a criterion: 3.5 hours per night.

Secondary objective:

- Identify the characteristics of patients that influence the development of their CPAP treatment plan.
- Develop an individualized plan to improve adherence based on the patient's profile and personal characteristics.
- Use telemonitoring for patients at risk of low adherence to improve compliance.

EXPECTED RESULTS

- Adherence is multidimensional and this implies the development of an individualized plan. (Rotenberg, Murariu, Pang, 2016; Sawyer, Gooneratne, Marcus, Ofer, Richards, Weaver, 2013; Ibarra, Morillo, Rudi, Ventura, Navarro, 2013).
- Adherence improves when patient characteristics, disease characteristics, technological factors, clinical factors such as side effects, psychological factors, and social factors are taken into account. (Rotenberg, Murariu, Pang, 2016)
- Influence on adherence to mood, perception of self-efficacy and expectations. (Orruño, Asua, 2016).
- The actions carried out at the beginning of treatment are key to improving adherence. (Orruño, Asua, 2016; Rotenberg, Murariu, Pang, 2016).
- Educational actions improve adherence results, without negative effects. (Rizk AK, Wardini R, Chan-Thim E, Bacon SL, Lavoie KL, Pepin. 2015)

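### Improvement is assigned to within-arm paired t-tests; the between-arm test that could answer the hypothesis is listed but not named primary and has no outcome form, day or sidedness

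*Combined protocol and SAP*

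**What the plan says.** The Hypothesis section is comparative: it states that "this stratification improves adherence to CPAP treatment of sleep apnea". The main goal is adherence, for which "the definition of adherence / compliance with SEPAR is taken as a criterion: 3.5 hours per night". The list of variables names adherence and quality of life as the dependent variables.

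Under Analysis of results, the first test listed for the hypothesis is "T-tests of means of related samples (to know if through the different interventions there are improvements in adherence and quality of life". Lower in the same section comes "Independent samples t-test (know the significance associated with the differences between the two interventions", and then an ANOVA of intervention type combined with another categorical variable. No test is called primary. The t-test line gives no outcome, outcome form, day or sidedness, and the section has no multiplicity rule.

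On timing, Monitoring and control of adherence says: "All measurements will be performed in 4 times: Day 1 - Day 30 - Day 60 - Day 90 – Day 180". That is five days under a count of four, and none is marked as the analysis day.

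The Sample size section sets a type I error of 0.05 and power of 0.80, without stating sidedness in the readable text. It reports that "we observed effect size values around 0.50", gives about 33 per group as the number needed, and says that "a number of 35 subjects per group is established" to allow for dropout. It then states a design effect size of d = 0.60.

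**The concern.** A paired test asks whether one arm changed over time. Both arms may change because patients get used to the device, because early problems are solved or because less motivated patients leave. None of this separates PIMA from Control.

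For adherence the paired test is weaker still. Control is the group "which will start treatment with regular CPAP WITHOUT stratification", and PIMA also begins CPAP within the study. There is no CPAP use before treatment to serve as a baseline, so the test compares two on-treatment days. Quality of life can have a Day 1 value, but its paired test is still not a comparison with Control.

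Because no test is primary and no day or form is fixed, the conclusion could rest on a significant change in PIMA alone, or on whichever day or form of adherence gives p < 0.05. The missing test specification also decides whether the stated 80% power applies to the comparison that matters.

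**Working it through.** **1. Reproducing the plan's 33 per group.** Inputs from Sample size: alpha 0.05, power 0.80, effect sizes 0.50 and 0.60. The normal formulas are n per arm = 2[(z_alpha + z_power)/d]² for two arms and n = [(z_alpha + z_power)/d]² for paired data, with z_power = 0.842 and z_alpha = 1.960 (two-sided) or 1.645 (one-sided).

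- Between arms, two-sided: 2(2.802/0.50)² = 62.8, so 63; 2(2.802/0.60)² = 43.6, so 44. With the t distribution: 64 and 45.
- Between arms, one-sided: d = 0.50 gives 50 (t: 51); d = 0.60 gives 2(2.486/0.60)² = 34.3, so 35 (t: 36, since the exact solution is 35.04).
- Paired, two-sided, d = 0.50: (2.802/0.50)² = 31.4, so 32 (t: 34).

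Two of these come within 2 of 33 by the normal formula: a one-sided between-arm test at d = 0.60 and a two-sided paired test at d = 0.50. A two-sided between-arm test gives 33 at neither effect size.

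**2. Power at the planned size.** Noncentral t, alpha 0.05. The noncentrality is d√(n/2) with 2n − 2 degrees of freedom between arms, and d√n with n − 1 for paired data. Example: d = 0.60, n = 35 gives noncentrality 2.510 against critical values of 1.995 (two-sided) and 1.668 (one-sided).

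| Test | d | 33 per arm | 35 per arm |
|---|---|---|---|
| Between arms, two-sided | 0.60 | 67.0% | 69.7% |
| Between arms, two-sided | 0.50 | 51.6% | 54.1% |
| Between arms, one-sided | 0.60 | 77.8% | 80.0% |
| Between arms, one-sided | 0.50 | 64.2% | 66.5% |
| Paired, two-sided | 0.50 | 79.5% | 82.0% |

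With 35 per arm, a two-sided between-arm test needs d = 0.68 for 80% power.

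**3. Reading superiority from paired tests.** Assume the same true standardised change (dz, mean change divided by the SD of change) in both independent arms, with n = 35 and two-sided 0.05. The probability that PIMA improves significantly and Control is not significant is the product of the two probabilities. The documents give no value of dz, so a range is shown.

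| dz | 0.1 | 0.2 | 0.3 | 0.35 | 0.4 | 0.5 | 0.6 |
|---|---|---|---|---|---|---|---|
| PIMA only | 8% | 17% | 24% | 25% | 23% | 15% | 6% |

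**4. Choosing among days.** Assume no true effect and a two-sided 0.05 between-arm t-test of adherence at each of Days 30, 60, 90 and 180, with 35 per arm. A simulation of 100,000 trials with equal correlation between days gave:

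| Correlation | 0.5 | 0.7 | 0.8 | 0.9 |
|---|---|---|---|---|
| Any day significant | 16% | 13% | 11-12% | 10% |
| Any day favouring PIMA | 8% | 7% | 6% | 5% |

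If the days were independent, the figures would be 1 − 0.95⁴ = 18.5% and 1 − 0.975⁴ = 9.6%. One pre-specified two-sided test gives 5% and 2.5%. The correlations are assumptions.

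**5. Outcome form.** If adherence is analysed as the proportion reaching 3.5 hours, the figures in step 2 do not apply. For assumed rates of 50% v 70%, 60% v 80% and 65% v 85%, two-sided power with 35 per arm is about 40%, 45% and 49%.

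**The case against.** The plan lists different tests for different questions: paired tests for change over time, the independent t-test for the difference between interventions. The second is the comparative question, and the ANOVA is a further between-arm analysis. A reader might infer that the plan has no between-arm test, or that it will declare PIMA superior on paired tests. The documents support neither. What stands is the lack of ranking and specification: the one line that names the outcomes is the paired one.

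A reader might also infer an uncontrolled choice between two outcomes. Adherence alone is the main goal, and quality of life is in none of the listed objectives, so that concern is small. The open choices are mainly the test, the form and the day.

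The 15-25% and 10-16% figures cost out practices that the plan permits but does not state, and they rest on assumed inputs. Outside the chosen range the first falls to 8% (dz 0.1) or 6% (dz 0.6).

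On power, the directional hypothesis could suggest a one-sided test, and 33 also fits a paired calculation. A figure in the Sample size section is not shown and may state the basis. It is therefore not established that the authors used the wrong test for sample size. Even so, that figure would probably not settle the outcome form, day or primary status of the analysis.

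**Conclusion.** The point holds as one of specification and ranking. The plan contains a test that can answer its hypothesis but does not make it govern the conclusion, and it leaves the form of adherence, the day and the sidedness open. It should be corrected before data are analysed.

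The firmest figures are those on power, which use the plan's own inputs. A two-sided between-arm t-test does not reach 80%: it has 70% at d = 0.60 and 54% at d = 0.50 with 35 per arm, or 67% and 52% with 33. Of the tests in the power table, about 80% is reached only by the one-sided between-arm test at d = 0.60 with 35 per arm (78% with 33), or by the two-sided paired test at d = 0.50 with 33 (79.5%; 82% with 35). The latter is not the comparative test. These figures apply to mean hours, not to a proportion.

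The false-claim rates of about 15-25% (paired reading) and 10-16% (four days; 5-8% favouring PIMA) show what the open wording allows. They do not predict what the sponsor would do.

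**What to change.** Name one primary analysis: a two-sided 0.05 between-arm comparison of adherence at one pre-specified listed day, with every allocated patient analysed in the assigned arm. Reconcile the count of four times with the five days listed.

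The sponsor should state the day and the form. Mean hour-meter hours per night fits the listed t-test; the proportion reaching 3.5 hours per night is then a key secondary analysis. If the proportion is made primary, use a test of proportions and recompute the power. Make the other days and quality of life secondary, and the paired tests descriptive only.

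For mean hours, restate two-sided power as 70% at d = 0.60 and 54% at d = 0.50 with 35 per arm (67% and 52% with 33), and state the basis of the 33.

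The cost is mainly wording, since the hour-meter data are already planned. The stated power becomes less favourable, and the sponsor can no longer choose the day or form later. Keeping 80% two-sided would need 45 per arm (d = 0.60) or 64 (d = 0.50), before dropout. The chosen day must also fit the Schedule, which ends in December. Assuming a single calendar year, a patient who starts on 31 August reaches Day 90 on 29 November but Day 180 only on 27 February.

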PIMA1-JO-PR

Adherence and quality of life of CPAP for obstructive sleep apnea: a randomized controlled trial

Protocol ID: PIMA1-3450

Secondary IDs: 3450

Date of the protocol: 14 February 2018

Date of submission to the Ethics and Clinical Research Committee of the Hospital Universitario de La Princesa: March 12, 2018

Research project report

TITLE: *Study on the individualization of a plan to improve adherence based on stratification and the use of telemonitoring for sleep apnea with CPAP.*

Main researcher: [name], [name], [name].

Project type: Individual

Duration: 6 months

Summary (Objectives and Methodology)

Aim: 1 Improve the adherence of patients diagnosed with OSA to CPAP treatment; 2 Follow adhesion; 3 Optimize resources; 4 Comply with SEPAR regulations; Develop experience in telemonitoring along with stratification.

Methodology: Patients with OSA (referral cohort) will be included. All participants will have a diagnosis of OSA with objective tests and a comprehensive evaluation. A follow-up will be carried out with objective evaluation questionnaires and compliance results will be obtained with the measurement of the CPAP hour meter.

List of acronyms in this report

- CPAP- Continuous Positive Airway Pressure (English). Positive Pressure in the Airways (Spanish)
- COPD- Chronic Obstructive Pulmonary Disease
- FEV - Forced Expiratory Volume
- AHI- apnea-hypopnea index
- CHF - Congestive Heart Failure
- mMRC - Modified Medical Research Council. Dyspnoea scale
- PIMA - Individualized Adhesion Improvement Plan
- OSA - sleep apnea-hypopnea syndrome
- SEPAR- Spanish Society of Pneumology
- TM: Telemonitoring

Background section and current status of the issue

OSA is characterized by the appearance of repetitive episodes of obstructive apnea and hypopnea during sleep associated with daytime sleepiness. The severity of OSA is evaluated and classified according to the number of apneas and hypopneas per hour of sleep (apnea-hypopnea index-AHI). In our country, in a prevalence study carried out more than 10 years ago, it was estimated that 15-20% of the population suffered from OSA. The natural history of OSA is still poorly understood, but longitudinal studies show that untreated OSA is associated with increased risk of accidents, loss of quality of life, and increased cardiovascular mortality.

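### The arm comparison prespecifies no baseline adjustment; for quality of life, ANCOVA on the Day 1 score would add precision from data already planned

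*Combined protocol and SAP*

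**What the plan says.** The section on analysis of results gives the between-arm test as "Independent samples t-test (know the significance associated with the differences between the two interventions"). It names no covariate and does not say whether the variable compared is a follow-up value or a change from Day 1.

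Baseline comparability is handled by significance tests: "Study of initial homogeneity: categorical variables (χ^2) + associated effect size", with Student's t and a Levene correction for quantitative variables.

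The same list contains other methods:

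- paired tests within arms: "T-tests of means of related samples (to know if through the different interventions there are improvements in adherence and quality of life"
- an ANOVA to see whether "differences were due to the type of intervention in combination with some other categorical variable"
- a structural equation model of protection and risk factors
- correlations of gains: "Linear correlations (know the interrelation between the so-called gains or aspects of change of the 2 interventions"

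None is marked as primary.

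On the data available, the section on monitoring and control of adherence begins the schedule at Day 1: "All measurements will be performed in 4 times: Day 1 - Day 30 - Day 60 - Day 90", with Day 180 added. The variables section lists adherence and quality of life as dependent variables and age among the sociodemographic ones. The summary states: "All participants will have a diagnosis of OSA with objective tests and a comprehensive evaluation". The main goal is CPAP adherence with a criterion of 3.5 hours per night, and CPAP starts after allocation.

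**The concern.** With about 35 patients per arm, a prognostic baseline score can differ noticeably between the arms by chance. A homogeneity test does nothing about that. A non-significant result leaves the difference in the outcome comparison, and a significant one comes with no stated consequence.

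A covariate fixed in advance deals with it directly: it removes the linear effect of the imbalance and reduces residual variance. For quality of life the natural covariate, the Day 1 score, is already scheduled. At stake are power that costs no patients and an effect estimate less exposed to the particular imbalance that occurs.

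**Working it through.** **Inputs.** From the sample size section: type I error 0.05, power 0.80, design effect d = 0.60, about 33 per group needed, 35 recruited. Sidedness is not stated. Assumed, because the documents give no value: correlation r between Day 1 and follow-up quality of life of 0.2 to 0.6, equal SDs at both times, and 2% to 9% of the variance of CPAP hours explained by AHI and age.

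**1. The plan's own figure.** Normal approximation for two independent means: n per arm = 2(z₁ + z₂)²/d².

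- d = 0.60, one-sided: 2(1.645 + 0.842)²/0.36 = 34.3, so 35. This is within 2 of the stated 33.
- d = 0.60, two-sided: 2(1.960 + 0.842)²/0.36 = 43.6, so 44 (45 by the t distribution).
- d = 0.50, two-sided: 63 (64 by t).

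The stated size therefore reproduces approximately for a between-arm test only if it is one-sided with d = 0.60. The figures below are two-sided.

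**2. Unadjusted t-test.** Noncentral t, noncentrality d√(n/2), 2n − 2 degrees of freedom. For n = 35: 0.60 × √17.5 = 2.51, power 69.7%. For n = 33: 67.0%.

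**3. ANCOVA and gain scores, quality of life.** ANCOVA multiplies the variance by 1 − r², so the effective d is 0.60/√(1 − r²). A gain score multiplies it by 2(1 − r), so the effective d is 0.60/√(2(1 − r)).

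| r | d, ANCOVA | Power, 35 per arm | Power, 33 per arm | d, gain | Power of gain, 35 per arm |
|---|---|---|---|---|---|
| 0.2 | 0.612 | 71.4% | 68.8% | 0.474 | 49.9% |
| 0.4 | 0.655 | 77.0% | 74.5% | 0.548 | 61.7% |
| 0.5 | 0.693 | 81.5% | 79.2% | 0.600 | 69.7% |
| 0.6 | 0.750 | 87.1% | 85.1% | 0.671 | 79.0% |

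The ratio of ANCOVA to gain-score variance is (1 − r²)/(2(1 − r)) = (1 + r)/2, which never exceeds 1. Estimating one slope inflates the variance by about 1 + 1/(70 − 1 − 3) = 1.015. At r = 0.5 this lowers power from 81.5% to 80.9%.

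**4. What a homogeneity test lets through.** With 35 per arm and SD 1, the chance difference in a baseline variable has SD √(2/35) = 0.239.

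- An observed difference of 0.4 SD gives t = 0.4/0.239 = 1.67, p = 0.10: non-significant.
- A difference at least that large, in either direction, arises in about 9% of properly randomised trials of this size.
- It shifts the unadjusted follow-up comparison by r × 0.4. At r = 0.5 that is 0.20 SD, and 0.20/0.60 is one third of the design effect.

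**5. CPAP hours.** There is no pre-treatment value, so the candidate covariates are diagnostic AHI and age. Allowing for k = 2 estimated slopes, the variance factor is (1 − R²)(1 + k/(2n − k − 3)), with 1 + 2/65 = 1.031 for n = 35.

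| R² (assumed) | Variance factor | Effective d | Power |
|---|---|---|---|
| 2% | 0.98 × 1.031 = 1.010 | 0.597 | 69.2% |
| 4% | 0.96 × 1.031 = 0.990 | 0.603 | 70.1% |
| 9% | 0.91 × 1.031 = 0.938 | 0.620 | 72.4% |

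Against 69.7% unadjusted, the change runs from nil (marginally negative) to about 3 points.

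**The case against.** The best defence is that the unadjusted t-test is valid and the main outcome has little to gain. Most of this stands, and it rules out several stronger readings.

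- **That the plan biases the estimate.** A reader might infer this from step 4. Under proper randomisation the unadjusted difference is unbiased over allocations and the type I error holds. The 0.20 SD is error conditional on an imbalance that has been observed. The allocation in the stages section is predictable alternation by the prescribers, so systematic imbalance is possible. That is a separate design problem, and adjustment for measured covariates would not cure it.
- **That baseline values are used only for homogeneity tests.** The list also has paired tests, an ANOVA with a second factor and a structural equation model, and the t-test may be on gains. None of these is a prespecified adjusted arm effect: the ANOVA factor is unnamed, the paired tests are within arm, and the structural model is aimed at relations between factors and actions. If the t-test is on gains, Day 1 already enters, and the relevant comparison is the gain column in step 3.
- **That adherence would gain as much as quality of life.** It would not, as step 5 shows. Quality of life is a dependent variable but does not appear among the stated objectives.
- **That the low power of a homogeneity test measures the problem.** Its power against a true 0.4 SD difference is 38%, but that concerns a population difference. The shift in the estimate depends on the observed difference, for which the 9% frequency is the relevant figure.

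The defence does not supply a reason to leave the Day 1 quality-of-life score out of the arm comparison.

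**Conclusion.** The point holds for quality of life, as an improvement available from planned data rather than a validity error. Power for d = 0.60 goes from 70% to between 71% and 87% with 35 per arm, or from 67% to between 69% and 85% with 33 completers, over assumed correlations of 0.2 to 0.6. At the low end the gain is slight. ANCOVA is at least as precise as a gain-score test, apart from the negligible cost of one slope.

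The absence of a prespecified covariate is clear from the text. The size of the gain is not, because it rests on the assumed correlation, on equal SDs, and on the Day 1 score being taken before the arms' care diverges, which the plan does not state. For CPAP hours the case for adjustment is optional.

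**What to change.** In the analysis section:

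1. For quality of life, specify ANCOVA of the follow-up score on arm plus the Day 1 score, at a named time point. State that it applies whatever the baseline comparison shows, and that Day 1 is measured before the arms' care diverges.
2. Keep the independent-samples t-test as a supporting result, and say whether it uses follow-up values or gains.
3. Replace the homogeneity p-values with a descriptive baseline table by arm with standardised differences.
4. For CPAP hours, either leave the comparison unadjusted or fix diagnostic AHI and age in advance as covariates. If adherence is analysed as at least 3.5 hours per night, yes or no, use a binary-outcome model instead of ANCOVA.

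The cost is a few lines of text, with no new data, visits or patients. The allocation method needs its own remedy.
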